6.5.3 Vital Signs

The baseline value will be the last non-missing value taken on or prior to first dose of study drug.

In addition to the presentation by age groups 5 to < 12 years of age, 12 to < 18 years of age and overall, vital signs will also be presented for age groups 5 to < 8 years of age and 8 to < 12 years of age.

6.5.3.1 Clinical Measurements

Values and changes from baseline for vital signs (SBP, DBP, pulse rate and measurement for temperature) and percentiles of SBP, DBP and Pulse Rate compared to age and height norms (see Appendix 9.3 for Blood Pressures and Table 4 for Pulse Rate) will be listed and summarized, for each age group and overall, by treatment group and visit using mean, standard deviation, median, minimum and maximum. Summary of vital signs will be presented for each visit [visit 1, 3, 5, 7 and 8 (EoS)], and for EoT values.

2017 American Academy of Pediatric Clinical Practice Guidelines

For each scheduled post-baseline visit, shift tables from baseline to each post-baseline visit will be presented with respect to the changes from normal blood pressure to elevated blood pressure; stage 1 HTN, or stage 2 HTN, see Table 8. For the cut-off points (90th, and 95th percentiles) see 2017 American Academy of Pediatric Clinical Practice Guidelines.

Table 8Definitions of Blood Pressure Categories and Stages

Children Aged 1–<13 years	Adolescents Aged ≥13 years
Normal BP: <90th percentile	Normal BP: <120/<80 mm Hg (SBP < 120 mmHg and DBP < 80 mmHg)
Elevated BP: ≥90th percentile to <95th percentile or 120/80 mmHg to <95th percentile (whichever is lower)	Elevated BP: 120/<80 to 129/<80 mmHg $(120 \le \text{SBP} \le 129 \text{ mmHg and } \text{DBP} \le 80 \text{ mmHg})$
Stage 1 HTN: ≥95th percentile to <95th percentile + 12 mmHg, or 130/80 to 139/89 mmHg (whichever is lower)	Stage 1 HTN: 130/80 to 139/89 mmHg ($130 \le SBP \le 139$ mmHg or $80 \le DBP \le 89$ mmHg)
Stage 2 HTN: \geq 95th percentile + 12 mmHg, or \geq 140/90 mmHg (whichever is lower)	Stage 2 HTN: \geq 140/90 mmHg (SBP \geq 140 or DBP \geq 90 mmHg)

Table obtained from: 2017 American Academy of Pediatric Clinical Practice Guidelines, Table 3 Note: the age classification into children and adolescents in the Clinical Practice Guidelines (2017) differs from the definition used in the protocol

Summaries will be presented for SBP and DBP separately, for each age group and overall, by treatment group. See further details in Section 5.4.2.3: Conversion of Blood Pressure to Percentiles.

In addition, PR measurements will be compared to age-related norms [Fleming et al, 2011] according to the percentiles shown in Table 4. Each PR value will be categorized as either below the 1st percentile, between the 1st and 99th percentile (limits included) or above the 99th percentile. For each scheduled post-baseline visit, shift tables from baseline to each post-baseline visit will be presented with respect to the changes from PR to below the 1st percentile and above the 99th percentile.

Summaries will be presented, for each age group and overall, by treatment group for the number of subjects with PR values below and above the normal range, the normal range is defined as: $1^{st} - 99^{th}$ percentile.

Potentially Clinically Relevant (PCR) criteria

PCR criteria for SBP will be identified using the following criteria and cut-points:

- Hypertension SMQ [20000147] (narrow search), or
- 2017 American Academy of Pediatric Clinical Practice Guidelines:
 - o For subjects aged 5 <13 years: any SBP above the 95th percentile +12 mmHg or BP≥ 140/90 mmHg at a post baseline visit, and for subjects aged ≥13 years: BP ≥140/90 mmHg at a post-baseline visit, or

• Change in category from baseline (Normal or elevated BP or Stage 1 HTN) to post-baseline (Stage 1 HTN or Stage 2 HTN).

PCR criteria for DBP will be identified using the following criteria and cut-points:

- Hypertension SMQ [20000147] (narrow search), or
- 2017 American Academy of Pediatric Clinical Practice Guidelines:
 - o For subjects aged 5 <13 years: any DBP above the 95th percentile + 12 mmHg or BP≥ 140/90 mmHg at a post baseline visit, and for subjects aged ≥13 years: BP ≥140/90 mmHg at a post-baseline visit, or
 - Change in category from baseline (Normal or elevated BP or Stage 1 HTN) to postbaseline (Stage 1 HTN or Stage 2 HTN).

Using these criteria, a high and low flag will be created to indicate if values meet these conditions (i.e., SBP/DBP PCR values) or not (i.e., non-SBP/DBP PCR values).

For PR, the below criterion will be used to identify a PCR increase:

• PR above 99th percentile compared to age-related norms PR [Fleming et al, 2011] and ≥ 15 bpm change from baseline.

PCR for SBP, DBP and PR will be summarized, for each age group and overall, by treatment group.

Data obtained from the clinical measurements (SBP. DBP and PR) will be provided in listing format by country, site and subject for the SAF.

6.5.3.2 Self-Measurements

Similarly to the clinic vital signs measurements (Section 6.5.3.1), values and changes from baseline for self vital signs measurements (SBP, DBP, pulse rate) and percentiles of self-measurements SBP and DBP compared to age and gender norms will be listed and summarized at each visit using mean, standard deviation, median, minimum and maximum. The number and percentage of subjects outside reference ranges will be shown.

For the purpose of the analyses, the average self-measurement vital signs will be calculated using all values from the 2-days diary collection for the regular measurements. If all measurements are missing, then the average will be missing. Extra measurements will be listed only.

For shifts from baseline to each post-baseline visit the categories used for presentation were obtained from the 2017 (American Academy of Pediatric) Clinical Practice Guidelines. For each scheduled post-baseline visit, shift tables from baseline to each post-baseline visit will be presented. Categories are: normal blood pressure; elevated blood pressure; stage 1 HTN, and stage 2 HTN, see Table 8. For the cut-off points (90th, and 95th percentiles) see 2017 American Academy of Pediatric Clinical Practice Guidelines.

Potentially Clinically Relevant (PCR) criteria

PCR criteria for SBP will be identified using the following criteria and cut-points:

- Hypertension SMQ [20000147] (narrow search), or
- 2017 Clinical Practice Guidelines:
 - o For subjects aged 5 <13 years: Any SBP above the 95th percentile +12 mmHg or BP≥ 140/90 mmHg at a post baseline visit, and for subjects aged ≥13 years: BP ≥140/90 mmHg at a post-baseline visit, or
 - Change in category from baseline (Normal or elevated BP or Stage 1 HTN) to postbaseline (Stage 1 HTN or Stage 2 HTN).

PCR criteria for DBP will be identified using the following criteria and cut-points:

- Hypertension SMQ [20000147] (narrow search), or
- 2017 Clinical Practice Guidelines:
 - o For subjects aged 5 <13 years: Any DBP above the 95th percentile +12 mmHg or BP≥ 140/90 mmHg at a post baseline visit, and for subjects aged ≥13 years: BP ≥140/90 mmHg at a post-baseline visit, or
 - Change in category from baseline (Normal or elevated BP or Stage 1 HTN) to postbaseline (Stage 1 HTN or Stage 2 HTN).

Using these criteria, a high and low flag will be created to indicate if values meet these conditions (i.e., SBP/DBP PCR values) or not (i.e., non-SBP/DBP PCR values).

PR measurements will be compared to age-related norms [Fleming et al, 2011] according to the percentiles shown in Table 4. For each scheduled post-baseline visit, shift tables from baseline to each post-baseline visit will be presented with respect to the changes from PR to below the 1st percentile and above the 99th percentile.

For PR, the below criterion will be used to identify a PCR increase:

• PR above 99th percentile compared to age-related norms PR [Fleming et al, 2011] and ≥ 15 bpm change from baseline.

Tables for potentially clinically relevant vital signs will be produced using the same criteria described in Section 6.5.3.1.

Data obtained from the self-measurements (SBP. DBP and PR) will be provided in listing format by country, site and subject for the SAF.

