- h. SBPM will be measured once in the morning and evening during the 2-day weekend bladder e-diary collection period. SBPM measurements should start in the weekend prior to week -2 and be taken in the weekend prior to the indicated visit (or TC). SBPM will be measured on 2 consecutive days at 1 and 2 weeks after start of dosing with PED25 (day 1) and after up-titration to PED50, if not already covered by the scheduled SBPM. Measurements will be taken in the sitting position (when possible, otherwise supine, but always in the same position). Preferably, the right arm should be used. Subject should have been calm and without distress for at least 5 minutes. Morning measurement should be taken before IP intake and evening measurement should be taken prior to bedtime.
- i. Additional hematology, biochemistry and urinalysis (urinalysis dipstick) tests will be performed at visit 3/week 0 (baseline) and visit 8/week 14 (EoS) only if an AE related to hematology, biochemistry or urinalysis parameters occurred since the previous visit or at the discretion of the investigator.
- j. Urine pregnancy test will be performed for females of childbearing potential at all on-site visits.

Footnotes continued on next page

Sponsor: APGD

EudraCT number 2016-001767-37

- CONFIDENTIAL -

k. PVR volume will be assessed by ultrasonography at visit 3/week 0 (baseline), visit 5/week 4, visit 7/week 12 (EoT) and visit 8/week 14 (EoS). For each subject, the same method should be used throughout the study. The bladder should only be emptied when it was initially filled with preferably > 50% of the bladder capacity for age. Every attempt should be made to measure PVR volume within a minute of voiding. A PVR volume of ≤ 20 mL is sufficient and the assessment does not have to be repeated. If the PVR volume is > 20 mL, the PVR volume assessment should be repeated (filled with preferably > 50% of the bladder capacity for age). If the subject is unable to complete a second measurement, it is up to the investigator to judge whether it can be skipped (and write the reason in the case report form). At visit 3/week 0 (baseline), the lowest PVR volume result measured should be used to evaluate the exclusion criterion. In case the lowest PVR volume measured is > 20 mL at visit 3/week 0 (baseline), the subject should be excluded from the study.

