5.4.2.4 Pulse Rate in Relation to Age

Resting pulse rate will be compared to age-related norms [Fleming et al., 2011] according to the percentiles shown in Table 4.

Age	Percentile								
	1 st	10 th	25 th	50 th	75 th	90 th	99 th		
4-6y	65	81	89	98	108	117	131		
6-8y	59	74	82	91	101	111	123		
8-12y	52	67	75	84	93	103	115		
12-15y	47	62	69	78	87	96	108		
15-18y	43	58	65	73	83	92	104		

 Table 4
 Percentiles for Resting Pulse Rate in Relation to Age and Gender

Source: web appendix to the Fleming et al article (web table 5)

Each value of pulse rate will be categorized as either being above the age-specific 99th percentile or below the 1st percentile.

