6.10 Additional Conventions

6.10.1 Analysis Windows

The study protocol gives the overall study schedule and the permissible intervals for these visits expressed as the number of days relative to visit 3/baseline. The total time each subject will be in the study will not exceed 18 weeks with a maximum of a screening period of 4 weeks and a maximum of 14 weeks for the investigational period.

Analyses will not exclude subject data due to the subject's failure to comply with the visit schedule.

Visit Windows for Efficacy and Safety Parameters

CRF visit	Target day relative to Baseline (Visit 3, Day -1)	Analysis Window	Analysis visit
Bladder e-d	liary		
Visit 3	Last value prior to first dose	Day -7 to Day 1 (prior to first dose)	Baseline
Visit 4	Day 14	Day 7 to Day 21	Week 2
Visit 5	Day 28	Day 22 to Day 42	Week 4
Visit 6	Day 56	Day 43 to Day 70	Week 8
Visit 7	Day 84	Day 71 to Day 91	Week 12
ЕоТ	Day 84	Day 1 to \leq Last dose of double- blind study drug	ЕоТ
Acceptabili	ty questionnaires		
Visit 7	Day 84	Day 71 to Day 91	Week 12
ЕоТ	Day 84	Day 1 to \leq Last dose of double- blind study drug	ЕоТ
SBPM			
Visit 3	Last value prior to first dose	Day -7 to Day 1 (prior to first dose)	Baseline
Visit 4	Day 14	Day 7 to Day 21	Week 2
Visit 5	Day 28	Day 22 to Day 42	Week 4
Visit 6	Day 56	Day 43 to Day 70	Week 8
Visit 7	Day 84	Day 71 to Day 91	Week 12
ЕоТ	Day 84	Day 1 to \leq Last dose of double- blind study drug	ЕоТ
Table contin	nued on next page		

All the assessments will be allocated to CRF visit based on Table 10.

CRF visit	Target day relative to Baseline (Visit 3, Day -1)	Analysis Window	Analysis visit	
Vital signs				
Visit 1			Screening	
Visit 3	Last value prior to first dose	Day -7 to Day 1 (prior to first dose)	Baseline	
Visit 5	Day 28	Day 22 to Day 56	Week 4	
Visit 7	Day 84	Day 57 to Day 91	Week 12	
ЕоТ	Day 84	Day 1 to \leq Last dose of double- blind study drug	ЕоТ	
Visit 8 [#]	Day 98	Day 92 or EoT + 1 to no more than 17 days after EoT	Week 14 (EoS)	
ECG	-			
Visit 1			Screening	
Visit 3	Last value prior to first dose	Day -7 to Day 1 (prior to first dose)	Baseline	
Visit 5	Day 28	Day 22 to Day 56	Week 4	
Visit 7	Day 84	Day 57 to Day 91	Week 12	
ЕоТ	Day 84	Day 1 to \leq Last dose of double- blind study drug	ЕоТ	
Clinical Lab	ooratory Tests (Hematology, B	iochemistry and Urinalysis)		
Visit 1			Screening	
Visit 3	Last value prior to first dose	Day -7 to Day 1 (prior to first dose)	Baseline	
Visit 5	Day 28	Day 22 to Day 56	Week 4	

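### Home blood pressure and pulse are averaged over pre-dose mornings and post-dose evenings, so no described table isolates post-dose values, and readings soon after a dose change appear to be listed only

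*SAP*

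**What the plan says.** Home readings are taken once in the morning, before study drug, and once before bedtime, on each of two weekend days (Protocol 7.2.3.2; SAP 5.4.2.2). Study drug is taken once daily in the morning (Protocol 1.1, Mode(s) of Administration). A complete visit therefore has four readings, and on treatment two are pre-dose and two post-dose.

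For analysis, SAP 6.5.3.2 states that "the average self-measurement vital signs will be calculated using all values from the 2-days diary collection for the regular measurements". It adds "If all measurements are missing, then the average will be missing" and "Extra measurements will be listed only". It describes no split by time of day.

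Protocol Table 1, footnote h, also requires home readings "measured on 2 consecutive days at 1 and 2 weeks after start of dosing with PED25 (day 1) and after up-titration to PED50", where the scheduled readings do not already cover those times.

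The potentially clinically relevant (PCR) criteria for home readings include "Any SBP above the 95th percentile +12 mmHg" and the matching diastolic rule. For pulse the criterion is "PR above 99th percentile compared to age-related norms PR" together with a change from baseline of at least 15 bpm. The pulse norms are in SAP Table 4, "Percentiles for Resting Pulse Rate in Relation to Age and Gender".

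**The concern.** Raised blood pressure and increased heart rate are identified risks of mirabegron in adults (Protocol 2.1.3). Blood pressure and pulse are a secondary safety endpoint, and Protocol 2.3 relies on home as well as clinic measurement to monitor both risks. A reader of the study report would want to know what these values look like some hours after a dose, and soon after the dose doubles from PED25 to PED50.

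As described, the tables cannot answer either question. The home tables blend trough with post-dose readings, and the clinic tables appear to be trough only. The weekends nearest to a change in exposure seem to go to listings. In addition, because the average is missing only when every reading is missing, a visit with mornings alone counts in full and may be compared with a baseline that includes evenings.

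**Working it through.** The plan gives no figure to reproduce on this point. The check sets the timing rules beside the summary rules and then gives the scale under stated assumptions.

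**1. Are clinic readings on treatment pre-dose?** Protocol 7.2.7 sets the order as ECG, vital signs, blood. Protocol 7.4 repeats that blood follows vital signs and ECG. Protocol 1.3.1 makes the week 4 and week 12 samples pre-dose troughs, with dosing in the clinic. No sentence says that clinic vital signs are pre-dose, but it follows under the standard schedule. Visits 1 and 3 precede the first dose and visit 8 follows the last. That leaves the evening home readings as the only scheduled same-day post-dose values.

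**2. How much of an evening effect survives averaging?** Let e be the evening drug effect and k·e the morning effect. The visit average shows (2ke + 2e)/4 = e(1+k)/2. The documents do not give k, so I assume 0 to 1.

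| k | Share kept | Loss if e = 5.1 bpm |
|---|---|---|
| 0 | 0.50 | 2.55 |
| 0.5 | 0.75 | 1.28 |
| 1 | 1.00 | 0 |

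The 5.1 bpm is the median 24-hour increase in Study 178-CL-203 (Protocol 2.1.2.2: single dose, 9 completers, no placebo group). It is used here only as a yardstick. k = 0 bounds the loss. The SAP's key terms put steady state at 10 days and the tablets are prolonged-release, so mornings from week 2 on are also on drug.

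**3. What does this do to the pulse criterion, if it is applied to the average?** In SAP Table 4 the gap from the 50th to the 99th percentile is 33, 32, 31, 30 and 31 bpm across the five age bands. From the 90th percentile it is 14, 12, 12, 12 and 12. The rise needed is max(15, gap): 30–33 bpm for a median child and 15 bpm for one at the 90th percentile. The evening rise that brings the average to that level is the needed rise × 2/(1+k):

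| k | Median child | Child at 90th percentile |
|---|---|---|
| 0 | 60–66 | 30 |
| 0.5 | 40–44 | 20 |
| 1 | 30–33 | 15 |

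A 15 bpm evening rise in a median child is flagged neither by single readings nor by the average.

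**4. What if readings are missing?** The weight on evenings is 2/4 = 50% when complete, 1/3 = 33% with one evening lost, and 0% with mornings only. If evening and morning baselines differ by d with no drug effect, a morning-only visit set against a four-reading baseline shifts the change by d/2. For an assumed d of 5–10 units that is 2.5–5 units.

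**5. Which weekends reach a table?** Regular on-treatment home readings belong to weeks 2, 4, 8 and 12. Footnote h adds weeks 1, 5 and 6; the week 2 reading is already regular. If the added ones are the extra measurements, 3 of 7 weekends (43%) enter no table in an up-titrated child, and neither do 2 of the 4 on PED50 (weeks 5 and 6 of 5, 6, 8 and 12). Visit 6 is on day 56 ± 3, and its diary covers roughly days 46 to 58. The added readings would fall near days 35 and 42, after up-titration near day 28.

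**The case against.** Averaging several noisy home readings is an ordinary summary. With complete data, baseline is averaged in the same way and every table is by randomised treatment group, with a blinded placebo arm. Any time-of-day shift from missing readings would also occur on placebo. Safeguards for both risks sit outside the averaging:

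- Individual values are listed (SAP 6.5.3.2).
- Clinically relevant diary changes become adverse events (Protocol 7.6).
- Raised blood pressure and increased heart rate are adverse events of special interest (Protocol 7.3.6), searched through standardised queries and tabulated (SAP 5.4.1, Table 2; SAP 6.5.1).
- The board reviews safety regularly (Protocol 10.4.1), and blood pressure stopping limits apply (Protocol 8.1).

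All of this stands. It limits the point to what the tables can show.

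Three stronger readings are tempting, and the documents do not support them:

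- A reader might infer that the SAP definitely leaves the readings after start and up-titration out of its tables. It never defines extra measurements. Protocol 7.2.3.2 also allows readings whenever the investigator wants them, and the term could mean only those. Footnote h sets the week 1, 5 and 6 readings apart from the scheduled ones, which makes the wider reading natural but not certain.
- A reader might infer that the pulse criterion certainly uses the average. SAP 6.5.3.2 refers to pulse measurements and to the criteria of 6.5.3.1, which categorises each value. Pulse is as ambiguous as blood pressure, so step 3 is conditional.
- A reader might infer that all on-treatment clinic values are trough. Under the crisis schedule (Protocol Appendix 12.13, Table 12) vital signs and ECG may be taken at a local clinic, or blood pressure and pulse at home. Blood sampling for pharmacokinetics is not allowed at an alternate clinic. Those values are not tied to a pre-dose sample.

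The table specifications that SAP 6.1 refers to were not available, and they may contain a split that the SAP does not describe.

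**Conclusion.** The point holds as a cheap improvement, with moderate confidence. No table described in the SAP or protocol isolates post-dose blood pressure or pulse. On the natural reading of an undefined term, the first tabulated PED50 values come from the diary before week 8. This weakens and delays a descriptive safety signal on an identified risk.

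It would be wrong to conclude that the plan hides a pulse effect or favours one arm. k is unknown, and an evening effect near the only paediatric figure would lose about 2.6 bpm at worst. The evening rises of 40–66 bpm that a median child would need for k between 0 and 0.5 are far above that figure. The practical stake is with children already near the upper percentiles, and with seeing the time course after up-titration.

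The conclusion assumes the standard visit order and no time-of-day split in the unseen table specifications. The statement about weeks 1, 5 and 6 also assumes that footnote h's added readings count as extra.

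**What to change.** Amend SAP 6.5.3.2 as follows:

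1. Keep the overall visit average.
2. Add a morning and an evening average per visit. Each is missing if its own readings are missing, and each is compared with its matching baseline. Use them in change-from-baseline and PCR tables of systolic pressure, diastolic pressure and pulse, by age group and treatment.
3. Define extra measurements. Summarise the protocol-scheduled ones under their own labels: start + 1 week, up-titration + 1 week and up-titration + 2 weeks. Keep them outside the home-reading Week 4 window in Table 10 ("Day 22 to Day 42"), which would otherwise mix PED50 readings with PED25.
4. State whether the blood pressure and pulse PCR criteria use single readings or averages.

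If the study report comments on trough timing of clinic vital signs or ECGs, limit that to visits with a documented pre-dose sample.

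The cost is extra tables from data already collected, with no new visit, reading or blood draw. It is not trivial, because SAP 6.5.3 asks for five age presentations of vital signs. Two-reading averages are also noisier. With between-reading correlation r, the SD ratio to the four-reading average is √[(r + (1−r)/2)/(r + (1−r)/4)]. That is 1.03 at an assumed r = 0.8 and 1.17 at r = 0.3, an increase of about 3–17%. The overall average has the better signal-to-noise once k exceeds 2/ratio − 1, about 0.71 (r = 0.3) to 0.94 (r = 0.8). It should therefore stay, with the split beside it.

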randomized. Subjects whose symptoms are not satisfactorily controlled with urotherapy and still fulfill the inclusion/exclusion criteria will enter the study. These subjects will be randomized to receive mirabegron in PED25 or placebo using a 1:1 ratio. Subjects with a body weight of \geq 35 kg are to receive the tablet unless unable to swallow tablets and would be provided the oral suspension as an alternative. Subjects with a body weight < 35 kg or those who cannot be dosed with the tablet will receive an oral suspension. Daily investigational product (IP) administration will start on day 1 (i.e., the day after this visit) and continue at this dose until visit 5/week 4 (i.e., for 4 weeks). Urotherapy will continue throughout the study treatment period until visit 7/week 12 (EoT).

At visit 5/week 4, dose up-titration to mirabegron in PED50 will be performed unless the investigator determines that the subject is adequately treated for OAB at the PED25 dose or if there are safety concerns identified and considered associated with the use of PED25. Dose down-titration from PED50 to PED25 can be done at any time thereafter for safety reasons.

Subjects will start with the subsequent 7-day bladder e-diaries approximately 7 days prior to the indicated visit (or TC).

Pharmacokinetic blood samples will be collected at visit 5/week 4 and visit 7/week 12 (EoT) as indicated in the Schedule of Assessments [Table 1].

• Follow-up period (2 weeks):

This period starts the day after visit 7/week 12 (EoT) and ends with visit 8/week 14 (EoS). The follow-up period is applicable to all subjects who have been randomized and received IP.

At visit 7/week 12 (EoT), IP administration will be stopped and a safety observation period of 2 weeks will start.

An independent DSMB will be established. A separate charter will describe the responsibilities of the DSMB.

A blinded interim analysis will be performed after 50% of children planned to be randomized have had their week 12/EoT assessment. The interim analysis will determine if the chance of a positive study with respect to the primary endpoint at the EoS is high enough to justify continuation of the study; otherwise, the study will be stopped for futility.

The IP will not be provided after study completion without written approval from the sponsor.

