The bladder e-diary, questionnaire results and other data collected in the e-diary will be transferred electronically to the sponsor or designee at predefined intervals during the study. The vendor will provide the sponsor or designee with a complete and clean copy of the study data. The ownership of this data is with the investigator and subsequently any changes requested to these subject-reported or nonsubject reported data will be made using the vendor's established process (e.g., a data clarification form to the vendor). The requested change must be supported by documented evidence at study site.

For this study the following information will be collected and entered by the subject or subject's parent(s)/legal guardian(s) in the e-diary (see [Sections 7.2.6 Acceptability and Palatability Questionnaire and 7.2.3.2 Self-measurement of Vital Signs] for detailed information per visit):

- Bladder e-diary:
 - Each day on weekend prior to week -2: volume measurements
 - Each day for 7 days before visit 3/week 0: micturition frequency
 - Each day for 7 days before visit 3/week 0: incontinence episodes
 - On the 2-day weekend period: volume measurements
- SBPM (blood pressure and pulse):
 - Each day of the 2-day weekend period: twice per day
 - On 2 consecutive weekend days at around 1 and 2 weeks after start of dosing with PED25 (day 1) and after up-titration to PED50, if not already covered by the scheduled SBPM
- Acceptability and Palatability Questionnaire:
 - On 1 weekend day preceding visit 7/week 12 (EoT)

The investigator must guide the subject and subject's parent(s)/legal guardian(s) to ensure that on the evening before and during the 2-day weekend period collection of volume, the subject's fluid intake should be regulated (as per investigator guidance) to an appropriate level considering, e.g., age, sex and subject's condition into account. The intake must remain as consistent as possible on these volume collecting days throughout the entire study.

- CONFIDENTIAL -

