Visit 7	Day 84	Day 57 to Day 91	Week 12	
ЕоТ	Day 84	Day 1 to \leq Last dose of double- blind study drug	ЕоТ	
Visit 8 [#]	Day 98	Day 92 or EoT to no more than 17 days after EoT	Week 14 (EoS)	
Post Void Residual (PVR) Volume				
Visit 3	Last value prior to first dose	Day -7 to Day 1 (prior to first dose)	Baseline	
Visit 5	Day 28	Day 22 to Day 56	Week 4	
Visit 7	Day 84	Day 57 to Day 91	Week 12	
ЕоТ	Day 84	Day 1 to \leq Last dose of double- blind study drug	ЕоТ	
Visit 8 [#]	Day 98	Day 92 or EoT to no more than 17 days after EoT	Week 14 (EoS)	

[#]Visit 8 may occur earlier due to early discontinuation as it is the last scheduled study visit.

For non-diary data, if a subject has more than one non-missing value within a visit window, the non-missing assessment which is closest to the target day within a window will be used. If two or more values are equally close and on different days, the latest non-missing value will be used. If two or more values are equally close and on the same day, the mean will be used for continuous variables or the worst observed case for categorical variables.

For diary data, the assessment date for the whole diary will be considered to be the date of the last valid day of the diary. If more than one diary has an assessment date within the same window, and if this results in more than one non-missing value of a diary variable, the non-missing value with the diary assessment day that is closest to the target day will be used. In case of ties on different days, the later non-missing value will be used. In case of ties located on the same side of the target day (i.e., more than one value for the same day), the mean of the values will be used for continuous variables and the worst value for categorical variables. For analyzing diary data the labels of the study visits will not be used, they will be assigned based on the dates of assessment.

A two-day window around the visit date will be applied for the assignment of study period for exposure data.

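### Home blood pressure and pulse sessions 1 and 2 weeks after up-titration appear to be listed only, so early or transient rises on PED50 are not tabulated

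*SAP*

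**What the plan says.** **Protocol.** Section 7.6 places the additional home sessions "On 2 consecutive weekend days at around 1 and 2 weeks after start of dosing with PED25 (day 1) and after up-titration to PED50", and shows that each session records pulse as well as blood pressure. Footnote h of the Schedule of Assessments makes them conditional: "and after up-titration to PED50, if not already covered by the scheduled SBPM". The protocol therefore treats them as separate from the scheduled sessions. The dose step itself is fixed in section 4.1: "At visit 5/week 4, dose up-titration to mirabegron in PED50 will be performed unless" the investigator judges the child adequately treated on PED25 or sees a safety concern.

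**SAP.** Section 5.4.2.2 gives the post-baseline SBPM visits as weeks 2, 4, 8 and 12, plus any reading the investigator thinks necessary. It does not mention the sessions after dose changes. Section 6.5.3.2 takes as the analysis value the average over the regular 2-day collection and then states: "Extra measurements will be listed only". The summaries, shift tables and PCR tables for home readings rest on that value.

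Table 10 in section 6.10.1 allocates assessments to analysis visits by date. For SBPM the Week 4 window is "Day 22 to Day 42" with target Day 28, and the Week 8 window is Day 43 to Day 70 with target Day 56. Where a window holds several values, "the non-missing assessment which is closest to the target day within a window will be used"; the separate rule for diary data also picks the value closest to target. Table 10 makes no exception for additional sessions.

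**The concern.** These sessions look at the child just after the dose changes. Protocol 4.2 sets target exposures of 69 and 188 ng·h/mL for PED25 and PED50, a ratio of 188/69 = 2.7. Increased blood pressure, increased heart rate and tachycardia are identified risks in adults (Protocol 2.1.3), and Protocol 2.3 names home measurement as one of the ways they will be monitored.

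Nothing else is scheduled to fill the gap. Clinic vital signs are taken at week 4 and then at week 12, and the week 8 contact is a telephone call. A child whose pulse or blood pressure rises in the first fortnight on PED50, and who then settles or returns to PED25, can look unremarkable at week 8. If the additional sessions are excluded, the home end-of-treatment value for a child who stops in weeks 5 to 7 can fall back to the week 4 session, recorded on PED25. The SAP provides a worst-post-baseline shift table for ECG (6.5.4) but none for SBPM.

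**Working it through.** No figure in the plan needs reproducing here. The check is visit-day arithmetic.

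**Inputs.** Visit 5 is on Day 28 ± 3 and visit 6 on Day 56 ± 3 (Protocol Table 1). Regular SBPM is taken on the weekend before the visit (footnote h). Windows come from SAP Table 10. I assume PED50 starts on the day of visit 5 or the day after.

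**Step 1: which sessions are additional.** For an up-titrated child the nominal post-baseline home sessions are at weeks 1, 2, 4, 5, 6, 8 and 12, seven in all. Regular sessions exist at weeks 2, 4, 8 and 12. That leaves 7 − 4 = 3 additional sessions (weeks 1, 5 and 6), and two of these are the only ones in the first fortnight on PED50.

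**Step 2: where the PED50 sessions fall by date** (PED50 start + 7 and + 14 days).

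| Visit 5 | PED50 start | 1-week session | Window (days from target) | 2-week session | Window (days from target) |
|---|---|---|---|---|---|
| Day 25 | 25 or 26 | 32 or 33 | Week 4 (4 or 5) | 39 or 40 | Week 4 (11 or 12) |
| Day 28 | 28 or 29 | 35 or 36 | Week 4 (7 or 8) | 42 or 43 | Week 4 (14) or Week 8 (13) |
| Day 31 | 31 or 32 | 38 or 39 | Week 4 (10 or 11) | 45 or 46 | Week 8 (11 or 10) |

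Because sessions are tied to weekends, actual days will shift slightly.

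**Step 3: first regular home session on PED50.** With visit 6 on Day 56 the preceding seven days are Days 49 to 55. Counted from a first PED50 dose on Day 29, that is 49 − 29 = 20 to 55 − 29 = 26 days. With visit 6 on Day 53 it is 17 to 23 days, and on Day 59 it is 23 to 29 days. At nominal timing neither additional session coincides with a regular one. At the extremes the 2-week session can: PED50 from Day 32 gives 32 + 14 = 46, and visit 6 on Day 53 opens the preceding week at 53 − 7 = 46.

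**Step 4: consequences under each reading of 6.5.3.2.**

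- *The sessions are extra.* They are listed. They enter no SBPM mean, shift table or reading-based PCR count.
- *The sessions are not extra.* The 1-week PED50 session falls in the Week 4 window, where the closest-to-target rule normally keeps the regular pre-visit reading and drops it. If the regular reading is missing, or its weekend falls before Day 22, a PED50 value is labelled Week 4. For example, with visit 5 on Day 25, a Thursday, the preceding weekend is Days 20 and 21, inside the Week 2 window.

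**Step 5: routes that do not depend on these sessions.** The blood pressure PCR definition includes the Hypertension SMQ, so a hypertension adverse event counts whichever reading prompted it. The pulse PCR definition needs a reading above the 99th percentile and a change of at least 15 bpm, and has no adverse-event limb.

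**The case against.** The strongest reply has three parts.

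First, *extra* is undefined. Since SAP 5.4.2.2 allows readings at the investigator's discretion, the word may mean only those. That is possible. It makes the text ambiguous rather than sound, and step 4 shows that Table 10 does not handle the sessions well on that reading either.

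Second, most clinically important rises are captured elsewhere. Protocol 6.6 ties down-titration to an adverse event possibly related to the drug. Clinically relevant e-diary changes are to be recorded as adverse events (7.6), and increased blood pressure and tachycardia are events of special interest (7.3.6). Dose decreases and interruptions are counted (SAP 6.3.1). Home readings are summarised at weeks 8 and 12 and at end of treatment, and clinic readings at week 12, end of treatment and end of study. All this stands, and it limits the gap to early or transient rises not reported as adverse events. A tachycardia event would appear in the adverse event tables but not in the pulse PCR table.

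Third, listing conditional sessions that differ between children is a common convention. That has some force, but the protocol schedules these sessions for everyone who changes dose, so they are more than incidental readings.

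A reader might go further and infer that rises after escalation never reach a table, or that the sessions are lost on every reading of the SAP. Neither is supported. Persistent rises are tabulated. If the sessions are not extra, a week 5 or 6 reading can become the end-of-treatment value, the Week 4 value when the regular one is missing, or a Week 8 candidate from Day 43 on.

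**Conclusion.** The point holds in a limited form. On the natural reading of SAP 6.5.3.2, three of seven nominal home sessions, including both in the first fortnight on PED50, are listed only. The first tabulated home reading on PED50 is the week 8 session, about 3 to 4 weeks after the step. Early or transient rises therefore enter no SBPM summary, shift or reading-based PCR table. The gap is wider for pulse, which has no adverse-event route into its PCR criterion. This rests on reading *extra* as the additional sessions and on roughly nominal visit timing.

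Three further inferences should be resisted. The documents give no rate for rises confined to weeks 5 and 6, so the number of children missed cannot be stated. Protocol 2.1.3 links greater risk to rising exposure at supratherapeutic doses, which does not establish a higher risk at this step. The SAP summarises vital signs by treatment arm and visit and plans no dose-specific conclusion, so a claim that the PED50 conclusion is biased towards safety goes beyond the text.

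It is worth correcting before database lock because the rule as written sets aside protocol-scheduled safety data on identified risks.

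**What to change.** 1. In SAP 6.5.3.2, define *extra measurements* as investigator-requested readings only, and reconcile that section with Table 10, including whether the additional sessions may supply the end-of-treatment value.
2. Add SBPM analysis time points for 1 week and 2 weeks after the dose step, assigned by date relative to the dose change and kept out of the Week 4 and Week 8 windows. Where a regular session already covers one of these points, let it serve for both.
3. Summarise blood pressure and pulse at these points by arm. The matching 25 mg and 50 mg placebo means placebo children go through the same apparent titration.
4. Derive the any-post-baseline SBPM PCR flags from all protocol-scheduled sessions, in the safety analysis set.

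The data are already collected and no procedure changes. The cost is SAP wording, a few more table rows, and somewhat higher PCR counts in both arms because more sessions are examined. The post-titration summaries cover only children who were up-titrated, a decision made after randomisation, so the comparison between arms at those points is descriptive.
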